7 SAFETY VARIABLES AND ANALYSES

7.1 Overview of safety analyses including subgroup analyses

Unless noted otherwise, the SS will be used for tables and listings of safety data.

Safety data described below will be listed.

In the event of permanent study treatment discontinuation, it is recommended to perform the safety assessments of Visit 8 within 7 days of the last DB study treatment intake. Although some subjects may be considered as being off study treatment, the time from the

last DB study treatment intake to the Visit 8 assessments is expected to be short. Therefore, for subjects who prematurely discontinue treatment, the safety data (laboratory tests, ECG, vital signs) measured within 7 days of the last DB study treatment intake will be included as being taken during DB study treatment. A subject who prematurely discontinues treatment may continue the planned study visits until EOS, without the run-out period. Therefore, for subjects who prematurely discontinue treatment, the safety data (laboratory tests, ECG, vital signs) measured more than 7 days from the last DB study treatment intake will be excluded from analyses.

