5.1.9 Premature discontinuation of study treatment

The decision to prematurely discontinue study treatment may be made by the subject, the investigator, or Idorsia personnel. The main reason for discontinuation must be documented in the eCRF and in the subject's medical charts (e.g., AE, lack of efficacy).

A subject has the right to prematurely discontinue study treatment at any time, without any justification, by withdrawal from study treatment only or by withdrawal from any further participation in the study (i.e., premature withdrawal from the study [see Section 8.2]). Although a subject is not obliged to give his/her reason for prematurely withdrawing from the treatment or the study, it is recommended that the investigator makes a reasonable effort to ascertain the reason(s), while fully respecting the subject's rights.

The investigator must discontinue study treatment for a given subject if, on balance, he/she believes that continued administration would be contrary to the best interests of the subject.

Study-specific criteria for discontinuation of study treatment are described in Section 5.1.10.

A subject who prematurely discontinues study treatment is NOT considered as withdrawn from the study and will be followed up until the planned EOS (Day 115), provided that the subject's consent for this limited participation in the study has not been withdrawn. The subject is recommended to return for safety assessments [see Table 1] within one week of his/her last DB study treatment intake (N.B., next day residual assessments will only be performed if the subjects can be assessed within 24 h of last DB study drug intake). All subjects withdrawn from study treatment are encouraged to follow planned study procedures (e.g., visits, sleep diary and questionnaire completion) until EOS. In this case, the run-out period (including Visit 9 and Visit 10) will not be performed, and subjects will directly enter the follow-up period after Visit 8 (considered as EOT in the event of premature discontinuation). The phone call will be performed as planned 30 days (+ 7 days) later, at Visit 11. This will decrease the amount of missing data which is important from a study integrity perspective. Subjects who prematurely discontinue study treatment or the study for any reason will not be replaced.

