7.1.2 Unscheduled visits

Unscheduled visits may be performed at any time during the study. Depending on the reason for the unscheduled visit (e.g., AE), appropriate assessments will be performed based on the judgment of the investigator. Results of ECGs and laboratory assessments, and changes in concomitant treatment will be recorded in the eCRF. After an unscheduled visit, the regular scheduled study visits must continue according to the planned visit and assessment schedule [Table 1].

Visit	SCREENING PHASE (20–31 days)								TREATMENT PHASE (82–86 days)								FU PHASE (30–37 days)						
	Screening period (7–18 days)				Run-in period (13–24 days)				Double-blind treatment (84 days ± 2 days ¹³)								Run-out period (7 days + 2 days)		FU period (23 days + 7 days) ¹⁷				
	1				2	3			4 ¹⁶	5 (phone call)	6				7	8				9	10	11 (phone call)	
Target Study Days						1 st night	2 nd night			1	7 to 14	1 st night ¹³ 27/28	2 nd night 28/29	55		1 st night ¹³ 83/84	2 nd night 84/85		85/86	92 (+ 2 days)	115 (+ 7 days)		
Evening(PM) / Morning (AM)		PM	AM		PM	AM	PM	AM				PM	AM	PM	AM		PM	AM	PM	AM			
MMSE ¹⁰	X																						
PGA-S ¹¹	X				X	X				←	-----	-----	-----	-----	-----	-----	-----	-----	-----			X	
PGI-C ¹¹ daytime symptoms					X					←	-----	-----	-----	-----	-----	-----	-----	-----	-----			X	
PGI-C ¹¹ night-time symptoms						X				←	-----	-----	-----	-----	-----	-----	-----	-----	-----			X	
PGI-S ¹¹	X				X	X				←	-----	-----	-----	-----	-----	-----	-----	-----	-----			X	
Patient Preferences ¹⁴										X							X						
Contact IRT	X				X					X				X					X				
Randomization ¹²										X													
Dispense IMP wallet(s)					X					X				X					X				
Study drug intake ³					←	-----	-----	-----	-----	-----	-----	-----	-----	-----	-----	-----	-----	-----	-----			→	
SAEs and AEs ⁵	←	-----	-----	-----	-----	-----	-----	-----	-----	-----	-----	-----	-----	-----	-----	-----	-----	-----	-----	-----	-----	-----	→

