1. For women of childbearing potential, serum test at V1 and V8 and urine test at V2, V4, V6, V7, V10. 2. The hand-held device is handed out to the subject and completed at home daily from V1 to V10. 3. Daily placebo single-blind treatment during run-in and run-out periods, and daily double-blind study treatment during treatment phase. 4. The 1st PSG can be performed any nights between V1 and V2. It includes assessment of AHI, PLMAI, SpO₂. 5. SAE and AE reporting and follow-up: all SAEs and AEs from signed ICF up to EOS. 6. In the event of permanent study treatment discontinuation, safety assessments of V8 are recommended to be performed within 7 days of last DB study drug intake. If the subject remains in the study, he or she will perform study visits and assessments as planned until EOS (Day 115), without the run-out period (including Visit 9 and Visit 10). 7. Approximately 30 to 60 minutes after PSG lights on. 8. Performed approximately 1 hour after lights on. 9. Height only at V1. 10. For elderly subjects only. 11. PGA-S, PGI-S and PGI-C (daytime symptoms and night-time symptoms questionnaires) will be completed at home once a week between V4 and EODBT. 12. Randomization will take place after all the V4 assessments have been performed and provided the subject fulfills all the eligibility criteria. 13. A time window of ± 2 days is allowed at each visit vs randomization visit (V4). 14. Patient preferences sub-study (PAUSE) available for sites in Germany and in the USA only. 15. In the event of permanent study treatment discontinuation, next day residual assessment of V8 will only be performed if the subjects can be assessed within 24 h of last DB study drug intake. 16. Three working days are required between V3 and V4 to obtain eligibility confirmation regarding objective sleep parameters. 17. If Run-out period exceeded by 2 days, then the follow-up period can only be exceeded by a maximum of 5 days.

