7.2.5 Laboratory assessments

7.2.5.1 Type of laboratory

A central laboratory (see central laboratory manual for contact details) will be used for all protocol-mandated laboratory tests until EOS, including follow-up tests due to abnormal laboratory findings and laboratory tests performed at unscheduled visits.

Local laboratory results of the parameters described in Section [7.2.5.2](#) will only be collected in exceptional circumstances (e.g., hospitalization of the subject due to a medical emergency). The local laboratory results (with the corresponding normal ranges) must be recorded in the eCRF.

If a central laboratory sample is lost or cannot be analyzed for whatever reason, it is recommended to the investigator to collect an additional sample as soon as possible for repeat analysis.

No repeat test is allowed if the subject does not meet the eligibility criteria.

Central laboratory reports will be sent to the investigator. In the event of specific (pre-defined) laboratory abnormalities, the central laboratory will alert Idorsia personnel and the concerned site personnel.

All laboratory reports must be reviewed, signed, and dated by the investigator or delegate within 10 working days of receipt and filed with the source documentation. The investigator/delegate must indicate on the laboratory report whether abnormal values are

considered clinically significant or not. Clinically significant laboratory findings present before signing of the ICF must be recorded on the Medical History page of the eCRF. Any clinically significant laboratory abnormalities detected after signing of ICF must be reported as an AE or SAE as appropriate [see Section 9], and must be followed up until the value returns to within the normal range or is stable, or until the change is no longer clinically significant.

Details about the collection, sampling, storage, shipment procedures, and reporting of results and abnormal findings can be found in the laboratory manual. Blood samples will be drawn under fasted condition (i.e., before breakfast) at Visit 3, Visit 6, Visit 7 and Visit 8.

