7.2 Adverse events

Unless noted otherwise, the AE summary tables will include treatment-emergent AEs (TEAEs): AEs that started or worsened on or after DB study treatment start date up to the earlier of 30 days after DB study treatment end date or the date of enrollment into the ID-078A303 extension study. An AE that started or worsened during any planned or unplanned study treatment interruption (e.g., run-out, safety follow-up) that is falling in the treatment-emergent time window defined above, will be considered as treatment-emergent.

AEs will be coded using MedDRA. The MedDRA version used for reporting will be specified in the footnote of the applicable output.

The number (%) of subjects experiencing a TEAE (including serious AEs [SAEs], AEs of special interest [AESIs] after adjudication by the Independent Safety Board [ISB], and AEs leading to premature discontinuation or temporary interruption of DB study treatment) will be summarized by SOC and/or PT, and/or maximum intensity.

Each AESI category (i.e., excessive daytime sleepiness, cataplexy, complex sleep behavior including hallucinations / sleep paralysis, suicide/self-injury, narcolepsy-like symptoms) will be summarized by PT separately.

A subject with multiple intensities reported for an AE will be summarized under the maximum intensity recorded for the event.

Apart from the summaries of occurrences, where each event is counted, a subject with multiple occurrences of an AE is counted only once in the AE category (e.g., SOC, PT). If a single AE worsens on the same treatment group, then this event will be considered as one occurrence. AEs will be sorted by descending frequency, first in the highest ACT-541468 dose level, then in the next highest ACT-541468 dose level, and finally in the placebo treatment group. After this sorting, SOCs are presented in alphabetical order with PT sorted within SOC in alphabetical order.

The following AE summary tables will be provided:

- Treatment-emergent AEs.
- Treatment-emergent AEs during the DB study period^a.

- AEs occurring (i.e., that started or worsened) during the Run-in period.
- AEs occurring (i.e., that started or worsened) during the treatment withdrawal period (based on the TWS).
- TEAEs during the DB study period^a related to study treatment.
- AEs leading to premature discontinuation of DB study treatment.
- AEs leading to temporary interruption of DB study treatment.
- Treatment-emergent SAEs (including occurrences).

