7.3 Laboratory tests

Laboratory analyses are based on data received from the central laboratory. Laboratory data will be converted into SI units. Unless noted otherwise, summaries and listings will include scheduled, re-test and unscheduled assessments.

Descriptive summary statistics for each scheduled visit (re-test excluded) will be provided for observed values and change from baseline in both hematology and blood chemistry laboratory parameters.

The change from baseline to last value (re-test and unscheduled assessments excluded) in the DB study period for hematology and blood chemistry parameters will be summarized.

Marked laboratory abnormalities are defined in [Table 4](#) below. The number (%) of subjects with marked laboratory abnormalities during DB study treatment will be tabulated. A subject will be counted only once, but may be reported in more than one marked laboratory abnormality criterion of a given parameter. Percentages will be based on the number of subjects at risk, i.e., those having at least one post-baseline value for a given parameter.

Shift from baseline to worst value post-baseline based on laboratory normal ranges will be provided for the following laboratory parameters:

- Liver enzymes: alanine aminotransferase (ALT), aspartate aminotransferase (AST), gamma-glutamyl transferase and total bilirubin (TBIL).
- Thyroid hormones: Thyroid-stimulating hormone, free T₃ and free T₄.
- Lipids: total cholesterol and triglycerides.
- Hematology: leukocytes, neutrophils, lymphocytes, eosinophils.

All laboratory data for subjects with at least one marked laboratory abnormality during DB study treatment will be listed. Any local laboratory data collected will be listed separately.

Table 4 Marked abnormalities in laboratory parameters for reporting

Laboratory parameter	Criteria for marked laboratory abnormalities
Hematology (SI unit)	
Hemoglobin (g/L)	< 100 < 80 > 20 above ULN or > 20 above baseline if baseline > ULN > 40 above ULN or > 40 above baseline if baseline > ULN
Hematocrit (%)	< 32% (Male); < 28% (Female) < 20% > 60% (Male); > 55% (Female) > 65%
Platelets (10 ⁹ /L)	< 75 < 50 > 600 > 999
Leukocytes (10 ⁹ /L)	< 3.0 < 2.0

Laboratory parameter	Criteria for marked laboratory abnormalities
	> 20.0 > 100.0
Neutrophils (10 ⁹ /L)	< 1.5 < 1.0
Eosinophils (10 ⁹ /L)	> 5.0
Eosinophils (%)	> 5%
Lymphocytes (10 ⁹ /L)	< 0.8 < 0.5 > 4.0 > 20.0
Reticulocyte (%)	> 2.5%
Blood chemistry (SI unit)	
ALT (U/L)	> 3 × ULN > 5 × ULN > 10 × ULN

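### SAP 7.1 excludes laboratory values taken more than 7 days after the last dose in early stoppers, and only a recommended visit secures a sample inside that window

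*SAP*

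**What the plan says.** SAP 7.1 sets two rules for laboratory tests, ECG and vital signs in subjects who stop double-blind (DB) treatment prematurely. Values "measured within 7 days of the last DB study treatment intake will be included as being taken during DB study treatment". Values "measured more than 7 days from the last DB study treatment intake will be excluded from analyses". The SAP supports the first rule by expecting the interval between the last dose and the Visit 8 assessments to be short.

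The in-window sample rests on a protocol recommendation. Protocol 5.1.9 states: "The subject is recommended to return for safety assessments", within a week of the last DB dose. Table 1, footnote 6 repeats it: "safety assessments of V8 are recommended to be performed within 7 days of last DB study drug intake". This applies whatever the stopping day. Subjects who stay in the study otherwise keep to the planned visits. Protocol 7.2.5.1 places fasting blood draws "at Visit 3, Visit 6, Visit 7 and Visit 8"; Visit 3 precedes randomization.

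SAP 7.3 ordinarily counts scheduled, re-test and unscheduled samples. Its percentages for marked abnormalities use only subjects with a post-baseline value for the parameter. The detailed listing has the same on-treatment trigger: "All laboratory data for subjects with at least one marked laboratory abnormality during DB study treatment will be listed".

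For adverse events the SAP uses a longer window. SAP 7.2 defines treatment-emergent events as "AEs that started or worsened on or after DB study treatment start date up to the earlier of 30 days after DB study treatment end"; extension enrolment closes that window if it comes sooner.

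**The concern.** The exclusion is firm, but the visit meant to make it harmless is optional. Take a subject whose last dose is on Day 12, who skips the recommended visit and then attends Visit 6. The sample on Day 29 comes 17 days after the last dose. If ALT is above 5 × ULN in that sample, the SAP 7.3 tables do not count it, it does not trigger the marked-abnormality listing, and the subject is not in the denominator.

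Attending the early visit does not fully close the gap. Protocol 7.2.5.1 requires clinically significant abnormalities to be followed until they return to normal, stabilise or cease to matter clinically. Suppose ALT is 4 × ULN on day 5 after stopping, and a re-test on day 10 shows 6 × ULN with bilirubin above 2 × ULN. The subject appears in the row for 3 × ULN but not in the row for 5 × ULN, nor in the combined ALT/bilirubin rows.

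The combined liver criteria concern rare findings, where one uncounted case can alter how the table reads. The samples would already have been taken and analysed.

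**Working it through.** The documents give no figure for how often a routine sample falls inside the window, so there is none to reproduce. The check is a direct count.

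**Inputs**
- Post-baseline laboratory visits: 6, 7 and 8 (Protocol 7.2.5.1). The laboratory rows of Table 1 are not readable in the copy used here.
- Target sample days: Visit 6 second morning, Day 29; Visit 7, Day 55; Visit 8 second morning, Day 85 (Table 1). Each visit may move ± 2 days.
- Last-dose day d for a premature stop: 1 to 83. Day 84 is the final planned dose.
- Window: 7 days (SAP 7.1).
- Early discontinuation: 14/356 = 3.9% over one month in Phase 2 (SAP 6.1.4). No Phase 3 rate is given, so 3.9% to 12% is assumed.
- Attendance q at the recommended early visit: not given, so it is varied.

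**Step 1: routine visits alone.** Gap = next routine sample day − d, in calendar days. The gap is 7 or less for:
- d = 22–28: 7 days
- d = 48–54: 7 days
- d = 78–83: 6 days

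Total inside: 20 of 83 (24%). Outside: 63 of 83 = 75.9%. With all visits two days early the share outside is 61/81 = 75.3%; with all two days late it is 65/85 = 76.5%.

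**Step 2: no usable post-baseline value.** For d = 1–21 even Visit 6 is too late: 21/83 = 25.3% of stopping days.

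**Step 3: allow for the recommended visit.** With stops spread evenly, share affected = 75.9% × (1 − q).

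| Attendance q | Share of early stoppers affected |
|---|---|
| 0 | 76% |
| 0.5 | 38% |
| 0.8 | 15% |
| 0.9 | 8% |
| 1 | 0% |

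**Step 4: numbers of subjects.** With about 600 subjects on active drug, early stoppers = 600 × 3.9% = 23.4 to 600 × 12% = 72.
- Nobody attends: 23.4 × 0.759 = 18 to 72 × 0.759 = 55.
- Half attend: 9 to 27.
- 80% attend: 4 to 11.

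These are upper bounds on subjects exposed to the rule. They ignore withdrawal from the study, after which there is no later sample to exclude, and they do not count abnormalities.

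**Step 5: would a 30-day window capture the next routine sample?** The longest gaps at target days are 29 − 1 = 28, 55 − 29 = 26 and 85 − 55 = 30, so yes at target days. It can fail within the visit window: with Visit 8 two days late, 87 − 55 = 32; with Visit 7 also two days early, 87 − 53 = 34.

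**The case against.** The strongest reply is that the schedule as written offers an in-window sample for every stopping day. Footnote 6, Protocol 5.1.9 and SAP 7.1 itself all recommend the Visit 8 assessments within 7 days, and unscheduled samples inside 7 days count too. This stands. A reader might infer that the schedule puts the next sample too late for three quarters of stopping days without qualification; that is true only of the routine visits.

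The rule also has a rationale. The protocol endpoint is marked laboratory abnormalities on DB treatment, and Protocol 3.2.1 says that 7 days covers more than five half-lives. This supports keeping the rule for on-treatment tables. It does not argue against a separately labelled count.

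A reader might infer that abnormalities disappear from the report. The documents do not support that. Clinically significant findings must be reported as adverse events, the central laboratory alerts sponsor and site to predefined abnormalities, and SAP 7.1 says that safety data will be listed. The adverse-event route is incomplete, however. It depends on the investigator's judgement, and SAP 13.3 says that events starting in safety follow-up are only listed, which sits badly with the overall treatment-emergent table in SAP 7.2.

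The 30-day comparison is also less clean than it looks. Several adverse-event tables cover only the DB study period, which for an early stopper ends at most one day after the last dose (SAP 12.2). The 7-day laboratory window is wider than that.

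A reader might also assume that early stoppers are the subjects likeliest to have drug-related abnormalities. Nothing in the documents shows this. Of the 14 Phase 2 stops in SAP 6.1.4, 4 were for adverse events (one of them on zolpidem), 7 were for other reasons and 3 had no reason given. A laboratory value that prompted the stop would precede it and would not be excluded as late.

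**Conclusion.** The point holds in conditional form. For early stoppers who miss the recommended visit and have no other sample within 7 days, SAP 7.1 excludes the next routine laboratory value for 63 of 83 stopping days. For 21 of those 83 days (Days 1–21) it also removes the subject from the at-risk denominator. Subjects who stop later can keep Visit 6 or Visit 7 values and stay in the denominator. Across all early stoppers the share affected lies between 0% and 76%, assuming evenly spread stops; attendance decides where. Late re-tests are excluded even when the early visit takes place.

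The 18 to 55 active subjects are a ceiling under assumed discontinuation rates, nobody attending and nobody withdrawing from the study. They should not be read as lost cases, and the documents do not allow an estimate of missed abnormalities. The on-treatment endpoint itself is sound. What is missing is a planned summary of safety samples collected after the window, which is a worthwhile and inexpensive addition.

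**What to change.** Leave the 7-day rule in place for by-visit statistics and on-treatment counts. In SAP 7.3:

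1. Add a separately labelled supplementary count of marked laboratory abnormalities and the elevated-liver criteria, using all post-baseline samples, including re-tests and unscheduled samples, up to 30 days after the last DB dose or extension enrolment.
2. Trigger the marked-abnormality listing from that count as well, and list any later scheduled sample, because the visit window allows gaps a few days beyond 30.
3. Report, by arm, how many early stoppers have a laboratory value within 7 days of the last dose. This shows how far the recommended visit worked.

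SAP 7.2 and 13.3 should also be reconciled on whether events starting in safety follow-up are tabulated or only listed.

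The cost is a short SAP addition and one extra table from data already collected. The added values are partly off drug and come almost only from discontinuers, so ascertainment can differ by arm if stopping rates differ. The table label should say so.

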7.2 Adverse events

Unless noted otherwise, the AE summary tables will include treatment-emergent AEs (TEAEs): AEs that started or worsened on or after DB study treatment start date up to the earlier of 30 days after DB study treatment end date or the date of enrollment into the ID-078A303 extension study. An AE that started or worsened during any planned or unplanned study treatment interruption (e.g., run-out, safety follow-up) that is falling in the treatment-emergent time window defined above, will be considered as treatment-emergent.

AEs will be coded using MedDRA. The MedDRA version used for reporting will be specified in the footnote of the applicable output.

The number (%) of subjects experiencing a TEAE (including serious AEs [SAEs], AEs of special interest [AESIs] after adjudication by the Independent Safety Board [ISB], and AEs leading to premature discontinuation or temporary interruption of DB study treatment) will be summarized by SOC and/or PT, and/or maximum intensity.

Each AESI category (i.e., excessive daytime sleepiness, cataplexy, complex sleep behavior including hallucinations / sleep paralysis, suicide/self-injury, narcolepsy-like symptoms) will be summarized by PT separately.

A subject with multiple intensities reported for an AE will be summarized under the maximum intensity recorded for the event.

Apart from the summaries of occurrences, where each event is counted, a subject with multiple occurrences of an AE is counted only once in the AE category (e.g., SOC, PT). If a single AE worsens on the same treatment group, then this event will be considered as one occurrence. AEs will be sorted by descending frequency, first in the highest ACT-541468 dose level, then in the next highest ACT-541468 dose level, and finally in the placebo treatment group. After this sorting, SOCs are presented in alphabetical order with PT sorted within SOC in alphabetical order.

The following AE summary tables will be provided:

- Treatment-emergent AEs.
- Treatment-emergent AEs during the DB study period^a.

- AEs occurring (i.e., that started or worsened) during the Run-in period.
- AEs occurring (i.e., that started or worsened) during the treatment withdrawal period (based on the TWS).
- TEAEs during the DB study period^a related to study treatment.
- AEs leading to premature discontinuation of DB study treatment.
- AEs leading to temporary interruption of DB study treatment.
- Treatment-emergent SAEs (including occurrences).
- Treatment-emergent SAEs related to study treatment (including occurrences).
- Disclosure to public database purposes: most frequent (threshold to be defined at time of reporting) non-serious TEAEs (including occurrences).
- Treatment-emergent AESIs after ISB adjudication.
- TEAEs during the DB study period^a related to abuse (as defined in the document *Search specifications for safety monitoring*).
- TEAEs during the DB study period^a based on selected Standardised MedDRA Queries or pre-defined search criteria (as defined in the document *Search specifications for safety monitoring*).
- TEAEs with fatal outcome.
- TEAEs related to study treatment with fatal outcome.
- Total number of deaths (those occurring on or after DB study treatment start date up to the earlier of 30 days after DB study treatment end date or the date of enrollment into the ID-078A303 extension study).

^a Includes only those TEAEs occurring (i.e., that started or worsened) during the DB study period [see Section 12.2].

All AEs will be listed as well as all deaths with cause of death. Any death will be listed using the SCR set. In addition, separate listings will be provided for SAEs.

An AE listing will be provided also for subjects who were not randomized (i.e., screen failures) and subjects who were randomized but did not take DB study treatment to report any subjects who discontinued run-in single-blind placebo treatment or discontinued the study, respectively, due to AE.

AEs submitted for adjudication will be listed flagging, separately, AEs that were adjudicated as an AESI and AEs that were considered an AESI by the investigator.

The number of subjects (including occurrences) with at least one case submitted for ISB adjudication will be summarized and listed.

An incomplete (day or month missing) or missing AE date will be imputed as described in the [Table 3](#). The ‘lower limit’ and ‘upper limit’ refer to the earliest and latest possible dates, respectively. As an example: If AE onset date is MAR2017 (day missing), the lower limit is 01MAR2017 and the upper limit is 31MAR2017; If AE onset date is 2017 (day and month missing), the lower limit is 01JAN2017 and the upper limit is 31DEC2017.

Table 3 Imputation rules for an incomplete or missing AE date

Field	Incomplete date	Missing date
AE resolution date	The upper limit.	No imputation; the AE is considered as ongoing.
AE onset date	
The rules below apply in the order presented:
 
1. If the (imputed) AE end date is on or after the start of DB study treatment, and if the DB study treatment start falls within the upper and lower limits (inclusive), the DB study treatment start date is used.2. If the (imputed) AE end date is on or after the start of run-in single-blind placebo treatment, and if the run-in single-blind placebo treatment start falls within the upper and lower limits (inclusive), the run-in single-blind placebo treatment start date is used.3. If the AE resolution date is missing, and:
a. if the DB study treatment start falls within the upper and lower limits (inclusive), the DB study treatment start date is used;else:
b. if the run-in single-blind placebo treatment start falls within the upper and lower limits (inclusive), the run-in single-blind placebo treatment start date is used.4. In all the other cases, the lower limit is used.	Whichever is the earlier of the AE resolution date or DB study treatment start date.

AE = adverse event; DB = double-blind.

The purpose of imputing AE dates is only to assign an AE to a specific treatment phase for the summary tables. No imputed date is considered in the medical evaluation of an AE.

